NCT03349996 Unique Protocol ID: ID3-20170704**PROTOCOL SYNOPSIS: BELSTREAM study**

| | | |
|---------------------------|--|---|
| Title | Belgian Physician-Initiated Trial Investigating the Lifestream Peripheral Stent Graft System for the treatment of complex TASC C and D iliac lesions | |
| Objective | The objective of this clinical investigation is to evaluate, in a controlled setting, the long-term (up to 60 months) safety and efficacy of the Lifestream Peripheral Stent Graft System (Bard) in clinical settings post CE-certification when used according to the indications of the IFU. | |
| Methodology | Prospective, multi-center, physician-sponsored clinical study | |
| Enrollment | 70 subjects | |
| Primary Endpoint | Efficacy endpoint | The primary endpoint of the study is primary patency at 12 months , defined as a target lesion without a hemodynamically significant stenosis on duplex ultrasound (>50%, systolic velocity ratio greater than 2.5) and with freedom from Target Lesion Revascularization (TLR) within 12 months. TLR is defined as a repeated intervention to maintain or re-establish patency within the region of the treated arterial vessel plus 5mm proximal and distal to the treated lesion edge. |
| | Safety endpoint | The primary safety endpoint of the study is the freedom of periprocedural Serious Adverse Events (SAEs), defined according to ISO 14155:2011 as any clinical event that is fatal, life-threatening, or judged to be severe by the investigator; resulted in persistent or significant disability; necessitated surgical or percutaneous intervention; or required prolonged hospitalization. |
| Secondary Endpoint | 1. | Primary patency rate at 1-, 6-, 24-, 36-, 48- and 60 month follow-up. Patients that present without a hemodynamically significant stenosis at the target area on duplex ultrasound (>50%, systolic velocity ratio greater than 2.5) and without prior TLR are defined as being primary patent at the given follow-up. |
| | 2. | Stent graft occlusion rate at pre-discharge, 1-, 6-, 12-, 24-, 36-, 48-, and 60-month follow-up. |
| | 3. | Ankle Brachial Index (ABI) at 1-, 6-, 12-, 24-, 36-, 48- and 60 month follow-up compared with the baseline ABI. |
| | 4. | Amputation rate at 1-, 6-, 12-, 24-, 36-, 48- and 60 month follow-up, defined as any amputation above the knee. |
| | 5. | Technical success, defined as the ability to achieve final residual angiographic stenosis no greater than 30%. |

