| | 6. | Clinical success at follow-up is defined as an improvement of Rutherford classification at 1-, 6-, 12-, 24-, 36-, 48- and 60 -month follow-up of one class or more as compared to the pre-procedure Rutherford classification. |
| Inclusion Criteria | General inclusion criteria | |
| | 1. | Corresponding to the CE-mark indications/contra-indications and according to the current medical guidelines for minimally invasive peripheral interventions. |
| | 2. | Patient presenting with a stenotic or occlusive lesion at the iliac arteries suitable for stenting (on indication for primary stenting, based on the discretion of the investigator) |
| | 3. | Patient presenting a score from 2 to 4 following Rutherford classification |
| | 4. | Patient is willing to comply with specified follow-up evaluations at the specified times for the duration of the study |
| | 5. | Patient is >18 years old |

| | |
|--|--|
| | 
6. Patient (or their legal representative) understands the nature of the procedure and provides written informed consent, prior to enrolment in the study
 
7. Patient is eligible for treatment with the Lifestream Peripheral Stent Graft System (Bard)
 |
| Angiographic inclusion criteria | |
| | 
1. The target lesion is either a modified TASC-II class C or D lesion with one of the listed specifications:
 
 ○ Type C lesions 
 ● Bilateral Common Iliac Artery occlusions ● Bilateral External Iliac Artery stenoses 3–10 cm long not extending into the Common Femoral Artery ○ Type D lesions 
 ● Unilateral occlusions of both Common Iliac and External Iliac Artery ● Diffuse disease involving the aorta bifurcation ● Bilateral occlusions of External Iliac Artery |
| | 
2. The target lesion has angiographic evidence of stenosis or restenosis post PTA >50% or occlusion which can be passed with standard guidewire manipulation
 |
| | 
3. There is angiographic evidence of a patent Common and Deep Femoral Artery
 |

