| Exclusion criteria | 
1. PTA is technically not possible (not feasible to access the lesion or a defect with the guidewire or balloon catheter)
 
2. Presence of an aneurysm immediately adjacent to the site of stent graft implantation
 
3. Lesions in or adjacent to essential collaterals(s)
 
4. Lesions in locations subject to external compression
 
5. Heavily calcified lesions resistant to PTA
 
6. Patients with diffuse distal disease resulting in poor stent graft outflow
 
7. Patients with a history of coagulation disorders
 
8. Patients with aspirin allergy or bleeding complications and patients unable or unwilling to tolerate anticoagulant/antiplatelet therapy and/or non-responders to anticoagulant/antiplatelet therapy
 
9. Fresh thrombus formation
 
10. Patients with known hypersensitivity to the stent material (L605) and/or PTFE
 
11. The target lesion is either a modified TASC-II class C or D lesion with aortic or common femoral lesion involvement: 
 ○ Type C lesions 
 ● Unilateral External Iliac Artery stenosis extending into the Common Femoral Artery ● Unilateral External Iliac Artery occlusion that involves the origins of the Internal Iliac and/or Common Femoral Artery ● Heavily calcified unilateral External Iliac Artery occlusion with the involvement of the Common Femoral Artery ○ Type D lesions 
 ● Infra-renal aortoiliac occlusion ● Iliac stenoses in patients with an Abdominal Aortic Aneurysm (AAA) requiring treatment and not amenable to endograft placement or 
 |

| | |
|---------------------|---|
| | 
other lesions requiring open aortic or iliac surgery
 
 Diffuse multiple stenoses involving the unilateral Common Iliac, External Iliac and Common Femoral Artery |
| 12. | Previously implanted stent(s) at the same lesion site |
| 13. | Reference segment diameter is not suitable for the available stent graft design |
| 14. | Untreatable lesion located at the distal outflow arteries |
| 15. | Use of alternative therapy (e.g. atherectomy, cutting balloon, DCB, laser, radiation therapy) as part of the index procedure |
| 16. | Patients refusing treatment |
| 17. | Patients for whom antiplatelet therapy, anticoagulants or thrombolytic drugs are contraindicated |
| 18. | Patients who exhibit persistent acute intraluminal thrombus of the proposed lesion site |

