| 19. | Perforation at the angioplasty site evidenced by extravasation of contrast medium |
| 20. | Patients with a history of prior life-threatening contrast medium reaction |
| 21. | Patients with uncorrected bleeding disorders |
| 22. | Female patient with child bearing potential not taking adequate contraceptives or currently breastfeeding |
| 23. | Life expectancy of less than twelve months |
| 24. | Any planned surgical intervention/procedure within 30 days of the study procedure |
| 25. | Any patient considered to be hemodynamically unstable at onset of procedure |
| P.I. | [name], ZNA Campus Stuivenberg, Antwerp, Belgium |
| Study conduct | The study will be conducted in accordance with the Declaration of Helsinki and ISO 14155:2011, and comply with requirements regarding Ethics Committees and any other applicable regulations |
| Participating sites | 
 A.Z. Groeninge, Kortrijk, Belgium: [name]Z. Sint-Blasius, Dendermonde, Belgium: [name] Hospital, Bonheiden, Belgium: [name]L.V. Hospital, Aalst, Belgium: [name]Z. H.H., Tienen, Belgium: [name]O.L., Genk, Belgium: [name]N.A. Stuivenberg, Antwerpen, Belgium: [name] |

Table 1. Study Investigations

| Time | | Tests and Procedures |
|---|----------------------|--|
| Pre-Procedure (up to 24 hours before procedure, unless otherwise noted.) | 1. 2. 3. 4. | Medical History Medication Registration Physical Exam Rutherford Categorization and ABI |
| Procedure | 1. 2. 3. 4. | Angiography, pre-procedure Study inclusion Intervention Rutherford Categorization and ABI |
| One day Post-Procedure | 1. 2. 3. | Medication Registration Physical Examination Rutherford Categorization and ABI |
| One month Follow-up (\pm 7 days) | 1. 2. 3. 4. | Medication Registration Physical Examination Rutherford Categorization and ABI Colour Flow Doppler Ultrasound |
| Six month Follow-up (\pm 30 days) | 1. 2. 3. 4. | Medication Registration Physical Examination Rutherford Categorization and ABI Colour Flow Doppler Ultrasound |
| One year Follow-up (\pm 30 days) | 1. 2. 3. 4. | Medication Registration Physical Examination Rutherford Categorization and ABI Colour Flow Doppler Ultrasound |
| Two year Follow-up (730 ± 30 days) | 1. 2. 3. 4. | Medication Registration Physical Examination Rutherford Categorization and ABI Colour Flow Doppler Ultrasound |

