| Three year Follow-up (1095 ± 30 days) | 1. 2. 3. 4. | Medication Registration Physical Examination Rutherford Categorization and ABI Colour Flow Doppler Ultrasound |
| Four year Follow-up (1460 ± 30 days) | 1. 2. 3. 4. | Medication Registration Physical Examination Rutherford Categorization and ABI Colour Flow Doppler Ultrasound |
| Five year Follow-up (1825 ± 30 days) | 1. 2. 3. 4. | Medication Registration Physical Examination Rutherford Categorization and ABI Colour Flow Doppler Ultrasound |

- Statistical Analysis Plan (SAP)

Descriptive data summaries will be used to present and summarize the collected data. For categorical variables (e.g. Gender) frequency distributions and cross tabulations will be given. For numeric variables (e.g. Patient age) minimum, maximum, mean, median and standard deviation will be calculated. For all variables a 95% confidence interval for the relevant parameters of the underlying distribution will be calculated. For all time-dependent events life-tables will be calculated using the Kaplan Meier estimate method, for a period starting on the date of the procedure up to and including the 60-month follow-up visit. Stratification to pre-procedural risk factors, Rutherford and lesion criteria will be performed and the log rank test will be used to compare between the different outcomes, associated p-values < 0.05 are defined as significant.

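### Technical success (secondary endpoint 5) does not require delivery and deployment of the Lifestream stent graft, so a failed delivery rescued with another stent is not counted as a device failure

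*Combined protocol and SAP*

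**What the plan says.** The objective in the protocol synopsis is to evaluate the "safety and efficacy of the Lifestream Peripheral Stent Graft System (Bard) in clinical settings post CE-certification". Enrollment is 70 subjects.

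Secondary endpoint 5 is the only definition of technical success: "Technical success, defined as the ability to achieve final residual angiographic stenosis no greater than 30" per cent. It names no device and sets no condition on delivery, deployment or what was implanted.

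Four other places bear on the question:

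- **General inclusion criterion 7:** "Patient is eligible for treatment with the Lifestream Peripheral Stent Graft System (Bard").
- **Exclusion criterion 1:** "PTA is technically not possible (not feasible to access the lesion or a defect with the guidewire or balloon catheter").
- **Exclusion criterion 15:** "Use of alternative therapy (e.g. atherectomy, cutting balloon, DCB, laser, radiation therapy) as part of the index procedure".
- **Table 1, Procedure row:** "Angiography, pre-procedure Study inclusion Intervention Rutherford Categorization and ABI", in that order.

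The Statistical Analysis Plan section opens with "Descriptive data summaries will be used to present and summarize the collected data" and promises 95% confidence intervals. It defines no analysis set and gives no rule for a failed device delivery or a substituted stent.

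**The concern.** The endpoint, as worded, measures whether the vessel was left open at the end of the procedure. The study asks how one particular stent graft performs. The two answers differ when the graft cannot be delivered or deployed and the operator finishes with another stent. The angiographic result may be good, but the study device did not produce it.

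Eligible lesions include bilateral common iliac occlusions, unilateral occlusions of both the common and external iliac arteries, and bilateral external iliac occlusions. Whether the device can be delivered is a fair question in such lesions, and technical success is the natural endpoint to answer it. What is at stake is the meaning of one secondary rate: the plan gives no way for a rescued delivery failure to lower it.

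**Working it through.** The plan states no technical success rate or target, so there is no figure to reproduce. The check has two parts.

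**1. Does any other text make a rescued case a failure?** Take a subject in whom the graft could not be delivered and a non-study stent left residual stenosis of 30% or less.

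- Endpoint 5: the sole criterion is met, so the case is a success.
- Inclusion 7: a suitability condition at entry, not an outcome rule.
- Exclusion 1: concerns reaching the lesion with guidewire or balloon catheter, not delivering the graft.
- Table 1: inclusion is listed before the intervention, so the subject is already enrolled when delivery fails.
- Exclusion 15: the examples name no stent, but the list is open. On a broad reading the subject is ineligible and may be removed, but is still not a failure.
- Statistical Analysis Plan: no rule.

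No provision turns the case into a failure.

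**2. How large could the effect be?** Inputs: n = 70 (Enrollment); b = number of subjects rescued with a non-study stent to 30% or less (not in the documents; 1 to 3 assumed); r = number left above 30% (not in the documents; 0 assumed first, then 2).

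- Literal rule: (n − r)/n
- Device-specific rule: (n − r − b)/n
- Rescued cases dropped: (n − r − b)/(n − b)

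Intervals are exact (Clopper-Pearson) 95%. When every case is a success the lower limit is 0.025^(1/n). For n = 70 this is 0.025^(1/70) = 0.949; for n = 67 it is 0.025^(1/67) = 0.946.

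With r = 0:

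| b | Literal | Device-specific | Dropped |
|---|---|---|---|
| 1 | 70/70 = 100% (94.9–100) | 69/70 = 98.6% (92.3–100.0) | 69/69 = 100% (94.8–100) |
| 2 | 70/70 = 100% (94.9–100) | 68/70 = 97.1% (90.1–99.7) | 68/68 = 100% (94.7–100) |
| 3 | 70/70 = 100% (94.9–100) | 67/70 = 95.7% (88.0–99.1) | 67/67 = 100% (94.6–100) |

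Each rescued case costs 1/70 = 1.4 percentage points, so the gap runs from 1.4 (b = 1) to 4.3 points (b = 3, 100 − 95.7).

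With r = 2 and b = 3, the literal rule gives 68/70 = 97.1% (90.1–99.7), the device-specific rule 65/70 = 92.9% (84.1–97.6), and dropping gives 65/67 = 97.0% (89.6–99.6). The two subjects left above 30% count as failures under all three rules. Only the three rescued cases go unregistered in the literal and dropped columns.

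**The case against.** The strongest reply is that a device-specific meaning is implied. The whole study concerns "safety and efficacy of the Lifestream Peripheral Stent Graft System", patients must be eligible for it, and an ability to reach a given residual stenosis can be taken as the ability of that device. The plan nowhere says that a rescued case is a success. This stands in part: the classification follows from the definition's silence, not from an explicit statement. But an implied condition leaves each of the seven listed sites to decide for itself, and the written criterion is met without the device.

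A second reply is that exclusion 15 already covers a substitute stent, since its examples are not exhaustive. That reading is open. It would keep the case out of the numerator, but out of the denominator too, so the device failure is lost, not counted.

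A reader might go further and infer that this is the only acute device endpoint, that it cannot register delivery failure at all, and that the reported rate will be biased towards 100%. The documents do not support this. Stent graft occlusion is assessed at pre-discharge (secondary endpoint 2), and periprocedural serious adverse events, including those requiring intervention, form the primary safety endpoint. A delivery failure left above 30% already fails endpoint 5. There is no distortion if no rescue occurs, and the documents give no rescue frequency.

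**Conclusion.** The point holds in a limited form. Endpoint 5 does not require the study graft to have been delivered and deployed. A failure rescued with a non-study stent to 30% or less is a success on the literal wording, or disappears on a broad reading of exclusion 15. It is not counted as a device failure either way.

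The overstatement is 1.4 to 4.3 percentage points for 1 to 3 rescued subjects out of 70. This assumes that all 70 reach 30% or less, that every subject had delivery attempted, and that the subject is the unit of analysis. The number of rescues is an assumption, not a forecast.

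The consequence is minor: the endpoint is secondary and descriptive, with no target or hypothesis test attached, and no primary conclusion depends on it.

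**What to change.** Reword secondary endpoint 5 and add a sentence to the Statistical Analysis Plan:

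1. Define technical success as delivery and deployment of the Lifestream stent graft at the intended site, with final residual angiographic stenosis of 30% or less.
2. Count replacement by a non-study stent after failed delivery or deployment as a technical failure. An additional stent placed beside a correctly deployed graft is not by itself a failure.
3. Use as denominator all enrolled subjects in whom delivery was attempted, so that such cases are not removed afterwards under exclusion 15.
4. State whether the unit is the patient or the lesion, because bilateral lesions are eligible.
5. Report residual stenosis of 30% or less by any means as a separate line, which keeps the current figure available.

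This changes how outcomes are classified, not how patients are treated. The cost is a few sentences, a slightly less favourable rate if rescues occur, and possibly one added procedure data field: Table 1 lists only the intervention and does not show that delivery, deployment or the device used is recorded.

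### Does the heading of exclusion 11 shut out the aortic-bifurcation lesion that angiographic inclusion 1 admits?

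*Combined protocol and SAP*

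**What the plan says.** Angiographic inclusion criterion 1 opens with "The target lesion is either a modified TASC-II class C or D lesion with one of the listed specifications" and then lists five lesion types, two under type C and three under type D. One of the type D entries is "Diffuse disease involving the aorta bifurcation".

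Exclusion criterion 11 opens with almost the same words but ends differently: "The target lesion is either a modified TASC-II class C or D lesion with aortic or common femoral lesion involvement". A colon follows, and then six lesion types, three under type C and three under type D. The type D entries are:

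- "Infra-renal aortoiliac occlusion"
- an entry that begins "Iliac stenoses in patients with an Abdominal Aortic Aneurysm (AAA) requiring treatment and not amenable to endograft placement or" and goes on to other lesions that need open surgery on the aorta or the iliac arteries
- "Diffuse multiple stenoses involving the unilateral Common Iliac, External Iliac and Common Femoral Artery"

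Lesion type returns in the Statistical Analysis Plan, which says "Stratification to pre-procedural risk factors, Rutherford and lesion criteria will be performed" and compares the strata with log rank tests. The synopsis plans 70 subjects and lists seven participating sites. The primary efficacy endpoint is primary patency at 12 months. The documents state no hypothesis and no performance goal for it.

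**The concern.** The two headings begin alike. The inclusion heading ties itself expressly to its list. The exclusion heading names a property of the lesion instead, and a lesion at the aortic bifurcation has that property on a plain reading. A site that took the heading as a rule in its own right would turn such patients away, while a site that took it as a caption would enrol them.

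With seven sites and 70 subjects (70 / 7 = 10 per site on average), a split in reading would make the lesion mix depend on site. In a single-arm study the mix feeds straight into the 12-month patency estimate. It also decides how many subjects fill the bifurcation stratum. Stratifying the analysis shows the bifurcation patients who were enrolled but not those who were refused.

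**Working it through.** The plan has no figure of its own to reproduce here. The check is a comparison of text under two readings, followed by a bound on size.

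**Reading A: the heading excludes by itself.** Of the five admitted types, the bifurcation lesion has aortic involvement. The other four are defined by iliac arteries alone, and one of them expressly stops short of the common femoral artery. So 1 of 5 admitted types (1 of 3 in type D) is both included and excluded.

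**Reading B: the heading introduces the list.** Setting the five admitted types beside the six excluded ones, no entry appears in both. The nearest is "Infra-renal aortoiliac occlusion", which is an occlusion and does not name diffuse bifurcation disease. So 0 of 5 admitted types are affected.

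**Which reading the text supports.**

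1. The exclusion heading ends in a colon and leads into type C and type D bullets, the layout used in angiographic inclusion 1, where the list defines the criterion.
2. The heading does not describe its own bullets exactly. The type C entry "Unilateral External Iliac Artery occlusion that involves the origins of the Internal Iliac and/or Common Femoral Artery" is met by involvement of the internal iliac origin alone, and the second type D entry reaches lesions needing open iliac surgery. Neither requires aortic or common femoral involvement. That suits a loose caption better than an operative rule.
3. Reading A leaves an expressly admitted lesion type with no eligible patient. Reading B gives every entry in both lists some effect.

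**Possible size, on assumed values only.** Let s be the share of bifurcation lesions among the 70 subjects, and d the difference between their 12-month patency and that of the rest. If all of them are enrolled rather than none, the overall estimate moves by s × d.

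| Assumed s | Assumed d (points) | Shift (points) |
|---|---|---|
| 7/70 = 10% | 5 | 0.5 |
| 14/70 = 20% | 10 | 2.0 |
| 28/70 = 40% | 20 | 8.0 |

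For scale, the 95% half-width at an assumed 90% patency is 1.96 × √(0.9 × 0.1 / 70) = 7.0 points.

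The table compares everyone enrolled with no one enrolled. The concern is that only some sites differ. If a fraction f of these patients is turned away and their places are filled in proportion from the other lesion types, the shift is f × s × d. With 2 of 7 equal-sized sites applying Reading A and the middle row above, it is (2/7) × 2.0 = 0.6 points.

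**The case for a change.** The strongest case for acting is that limiting words were at hand, since the inclusion heading has them, and the exclusion heading lacks them. The title speaks of iliac lesions, so a site could think that an exclusion for aortic involvement was meant. Eligibility defines the population, a clarifying sentence is cheap, and patients wrongly refused cannot be recovered later.

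Part of this stands. The ambiguity is real if the heading is read apart from its list, and nothing else in the documents states how the heading is to be taken. What exists is a synopsis, and whether a fuller text settles the point cannot be known from it.

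The argument does not carry further, for three reasons. The missing phrase and the literal scope of the heading are the main support for Reading A, against the colon, the parallel layout and the express admission of the lesion. The documents do not show that any site read the heading that way. A table of patency with and without bifurcation subjects would not meet the concern either: it contains only enrolled subjects, so it is as blind to refusals as the planned stratification that it would largely repeat. It would also set aside subjects who meet a listed inclusion type. At the same assumed 90% patency, dropping 7 subjects widens the half-width to 1.96 × √(0.09 / 63) = 7.4 points, and dropping 28 widens it to 1.96 × √(0.09 / 42) = 9.1 points.

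**Conclusion.** No change to the plan follows. The heading of exclusion 11 is loosely worded, and taken alone it reaches one of the five admitted lesion types. Read with its list, as the layout invites, it reaches none, and the two criteria fit together. A site following the plan would be expected to resolve the point that way without being told.

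The statistical consequence is small or unknown. Every input to the range of 0.5 to 8.0 points is assumed. Its top combines the two most extreme values and supposes that all sites switch reading together. Only that top end exceeds the 7.0-point half-width. No test of overall patency against a target is planned, so no such conclusion is at risk. Refusals at some sites would mainly make the bifurcation stratum smaller and its comparison less precise.

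This conclusion rests on the text of the synopsis and on the absence of any sign that sites differed. It takes no position on which lesions ought to be treated in the study.

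### Clinical success and ABI change make no allowance for revascularisation outside the iliac target segment, so gains from such procedures count in these secondary results

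*Combined protocol and SAP*

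**What the plan says.** All references are to the combined protocol and SAP.

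- **Outflow eligibility (Exclusion criteria 6 and 14; Angiographic inclusion criterion 3).** Item 6 excludes "Patients with diffuse distal disease resulting in poor stent graft outflow". Item 14 excludes an "Untreatable lesion located at the distal outflow arteries". Inclusion requires this much of the femoral vessels: "There is angiographic evidence of a patent Common and Deep Femoral Artery". Nothing is required of the superficial femoral, popliteal or tibial arteries.
- **Other procedures (Exclusion criteria 15 and 24).** Item 24 reads "Any planned surgical intervention/procedure within 30 days of the study procedure". Item 15 bars alternative therapies during the index procedure and gives an open list of examples. Neither addresses a planned procedure after 30 days or an unplanned one at any time.
- **Target-specific endpoints (Primary Endpoint; Secondary Endpoint 1).** TLR is a repeat intervention "within the region of the treated arterial vessel plus 5mm proximal and distal to the treated lesion edge". Patency is judged by duplex at the target and requires freedom from TLR.
- **Limb-level endpoints (Secondary Endpoints 3 and 6).** Endpoint 3 is "Ankle Brachial Index (ABI) at 1-, 6-, 12-, 24-, 36-, 48- and 60 month follow-up compared with the baseline ABI". Endpoint 6 begins "Clinical success at follow-up is defined as an improvement of Rutherford classification" and asks for at least one class relative to the pre-procedure value. Neither mentions other revascularisation.
- **Design and analysis (Methodology; Statistical Analysis Plan).** The study is a "Prospective, multi-center, physician-sponsored clinical study" of 70 subjects, with no comparator described. The SAP gives descriptive summaries, confidence intervals, Kaplan-Meier life-tables and log-rank tests. It has no rule for revascularisation elsewhere in the leg, and Table 1 does not list its recording.

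**The concern.** ABI and Rutherford class reflect flow through the whole leg, from the iliac segment to the foot. A patient whose symptoms do not improve after the stent graft, and who later has a femoropopliteal procedure and improves by one class, is a clinical success under endpoint 6. The later ABI likewise enters endpoint 3 as a change from baseline.

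The stated objective is the safety and efficacy of this stent graft. In a controlled comparison, procedures elsewhere might occur in both arms and partly cancel. Here nothing offsets them. Without a record of which limbs had such a procedure and when, a reader of the 6- to 60-month tables cannot separate improvement reached with the graft alone from improvement that followed treatment elsewhere.

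**Working it through.** **1. There is no plan figure to reproduce.** The enrolment of 70 has no derivation, and the documents give no expected success rate, ABI change or rate of other procedures. No stated figure is contradicted. What follows first traces the definitions and then sizes the effect under assumptions.

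**2. Tracing one patient through the definitions.** Take a patient with a focal, treatable superficial femoral lesion.
- Exclusion 14 does not apply, because the lesion is treatable. Exclusion 6 does not apply, because the disease is not diffuse with poor outflow. The femoral patency criterion can be met.
- Exclusion 24 does not reach a procedure planned for, say, month 3. An unplanned procedure is not addressed at all.
- The procedure lies beyond the target region plus 5 mm, so it is not a TLR and patency is unchanged.
- At the 6-month visit (± 30 days), endpoints 3 and 6 use the ABI and Rutherford class as they then stand.

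The 30-day bar largely shields the 1-month visit (± 7 days) from planned staged procedures, so the exposure is mainly from 6 months on.

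**3. Direction for endpoint 6.** At any visit:

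planned successes = (improved, no such procedure) + (improved, with such a procedure)

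The second term cannot be negative, so the planned rate is never below the rate reached without such a procedure.

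**4. Direction for endpoint 3.** Suppose new disease elsewhere lowers ABI by L and a later procedure restores d. The net effect on that limb is d − L. It is positive if the lesion was already there at baseline (L = 0), nil if d = L, and negative if d < L. The definitions do not fix the sign.

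**5. Size for clinical success (all inputs assumed).** Let s be success from the stent graft alone, f the share of the remaining patients who have a non-target procedure, and g the share of those who then gain a class. Added success = (1 − s) × f × g.

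| s | f | g | Added points | Of 70 patients |
|---|---|---|---|---|
| 0.90 | 0.25 | 0.5 | 0.10 × 0.25 × 0.5 = 1.25 | 0.9 |
| 0.80 | 0.25 | 0.5 | 0.20 × 0.25 × 0.5 = 2.5 | 1.8 |
| 0.80 | 0.50 | 0.8 | 0.20 × 0.50 × 0.8 = 8.0 | 5.6 |
| 0.70 | 0.50 | 0.8 | 0.30 × 0.50 × 0.8 = 12.0 | 8.4 |

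A simpler model multiplies the share of all patients with such a procedure (10–40%) by a gain of 10–20 points in their chance of success. It gives 0.10 × 10 = 1 to 0.40 × 20 = 8 points.

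**6. Size for ABI (all inputs assumed).** Share of patients × ABI gain = 0.10 × 0.10 = 0.01 to 0.40 × 0.20 = 0.08. This is the gross gain that enters the mean, before any offset L from step 4.

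**7. Sampling error for comparison.** For 56/70 (80%), the exact 95% interval is 68.7% to 88.6%, about ±10 points. For mean ABI change, 1.96 × SD/√70 is 0.035 at an assumed SD of 0.15 and 0.059 at 0.25. The assumed effects thus run from negligible to about the size of the sampling error or slightly above it. A larger sample would not reduce them.

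**The case against.** **Primary patency is haemodynamic and target-specific.** This stands. Patency is defined by a duplex velocity ratio and measured from 1 month on. A reader might infer that ABI and Rutherford class are the only haemodynamic evidence, or that the primary endpoint is compromised. Neither is so. ABI and Rutherford are the limb-level measures, and only they are affected.

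**Outflow treatment in the index session may already be barred.** A reader might infer that it is plainly allowed. The text does not support that: item 15 is an open list, and item 24 can be read to cover a planned procedure in the same session. The text is unclear, and the point does not depend on it.

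**The affected group is inferred.** Eligibility of treatable outflow lesions follows by implication from items 6 and 14, and item 6 and the femoral patency criterion narrow it. No frequency is given. This limits what can be said about size. It does not change what the definitions count.

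**The bias need not favour the device.** This stands for ABI (step 4). It does not stand for endpoint 6 measured against success without such a procedure (step 3).

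**Uneven bias across Rutherford strata.** A reader might infer this from the planned stratification. The log-rank comparisons follow the life-tables for time-dependent events and are not clearly meant for ABI change or visit-level Rutherford improvement, and nothing shows that outflow disease differs by class.

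**The case report form may already hold the data.** It is not shown, so this is possible. In that case only the reporting rule is missing.

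**Conclusion.** The concern holds for two secondary endpoints. As written, endpoint 6 counts improvement that follows revascularisation outside the target segment, and endpoint 3 includes the ABI measured after it. No comparator is described to offset either.

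Clinical success can only be raised relative to success reached without such a procedure. The net direction for ABI is uncertain, because a later procedure may only restore what new disease took away. The size is unknown. The ranges of about 1 to 12 points and 0.01 to 0.08 ABI rest wholly on assumed inputs and show what is possible, not what was observed.

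Primary patency and TLR are unaffected. The endpoints are descriptive, with no success threshold, so the change is worth making but does not touch the main result.

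**What to change.** 1. **Record** the date, limb and level of any revascularisation outside the target segment, at the index procedure and at each visit, if not already captured. Recording by limb matters because several eligible lesion types are bilateral.
2. **Endpoint 6:** keep it as planned. Beside it, report the proportion with at least one class of improvement and no such procedure on that limb, keeping patients who had one in the denominator as non-successes.
3. **Endpoint 3:** keep it as planned. At each visit, give the number of limbs with a prior non-target procedure and show ABI change with and without them as a descriptive sensitivity analysis. State that removing them may be selective: these may be the limbs doing badly, so the mean without them could be higher rather than lower.
4. **Interpretation:** attribute clinical success to the device only in light of the companion row.

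No visit, test, patient or eligibility rule changes. The cost is one data field and a few table rows. The companion success rate may be lower than the planned one, and it counts disease elsewhere in the leg against the graft, including in patients who had improved before the other procedure. It is therefore a cautious figure to read beside the planned rate, not a replacement for it.
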